1.4.4 Clinical Evaluations – IV Administration

The first questions that needed to be addressed when initiating studies evaluating ^{99m}Tc-Tilmanocept against new diagnostic targets using a new route of administration are: Can ^{99m}Tc-Tilmanocept specifically and sufficiently localize to aggregations of pathology related CD206 expressing macrophages to enable diagnostic imaging of disease associated inflammation, and what is the optimal imaging protocol to facilitate this desired imaging capability. In February of 2017, Navidea initiated the first such study evaluating these questions in which IV injected ^{99m}Tc-Tilmanocept was evaluated for localization in skeletal joints of subjects with skeletal joint inflammation due to rheumatoid arthritis (RA). As of this writing, this study in patients with active RA is still ongoing but has already provided positive affirmation that IV injected ^{99m}Tc-Tilmanocept localizes specifically and sufficiently to CD206 macrophages in RA inflamed joints with enough intensity to enable diagnostic imaging.

The study (Clincaltrials.gov number NCT02865434) was designed to determine an optimal imaging protocol utilizing IV injected ^{99m}Tc-Tilmanocept to visualize aggregations of CD206 expressing macrophages in skeletal joints inflamed due to involvement of rheumatoid arthritis (RA) and to evaluate safety variables. The study is expected to have 39 participants: 33 with active RA and 6 (healthy controls) without joint inflammation. Twenty-seven of the participants will be divided into 9 cohorts comprised of three participants each. The participants in each cohort will receive a different combination of tilmanocept mass dose labels with a different specific activity of ^{99m}technetium (^{99m}Tc) as described in Table 1.

Table 1. The RA Dose Matrix of 99mTc-Tilmanocept administration

Dose Matrix	50 μg Tilmanocept	200 μg Tilmanocept	400 μg Tilmanocept
10 mCi ^{99m} Tc	Cohort 1	Cohort 2	Cohort 3
5 mCi ^{99m} Tc	Cohort 4	Cohort 5	Cohort 6
1.0 mCi ^{99m} Tc	Cohort 7	Cohort 8	Cohort 9

Two additional cohorts of 6 participants each will be recruited and imaged using the selected optimal dose. One cohort (Cohort 10) will be comprised of individuals with active RA, while the other cohort (Cohort 11) will consist of healthy individuals without joint disease. In addition to imaging of skeletal joints that may be involved in RA, participants in Cohorts 10 and 11 with be evaluated for ^{99m}Tc-Tilmanocept biodistribution, dosimetry and blood plasma half-life.

Three more subjects remain to be injected and imaged in each Cohort 10 and Cohort 11. To date, no serious adverse events have been observed and no adverse events have been attributed to tilmanocept in this study.

Figure 6A and Figure 6B show examples of the kinds of imaging results that are being obtained in this study. Figure 6A shows that hands of a participant with active RA, while Figure 6B shows an image of an RA involved ankle of a different individual. In both figures, localization of ^{99m}Tc-Tilmanocept to RA inflamed joints is clearly visible.

Page 31 of 71

Confidential

Tc 99m tilmanocept Clinical Study Protocol Number: NAV3-30

[figure not shown]

Figure 6. IV Administered Tc 99m tilmanocept Localization to RA Joints

(A) 99m Tc-Tilmanocept localization in hands (small joints' detection area after 200 $\mu g/10$ mCi dose of 99m Tc-tilmanocept; picture on the left) and (B) in ankles and feet (50 $\mu g/10$ mCi dose of 99m Tc-tilmanocept; picture on the right) after injections of 99m Tc-tilmanocept administrated intravenously.

1.4.5 Clinical Safety using Intradermal, Subcutaneous, and Peritumoral Injections

Over 200,000 patients in clinical trials and commercial use in the U.S. for ILM with SLNB have been exposed to Tc 99m tilmanocept (Lymphoseek®), and there have been no safety signals, no deaths due to drug, and no Serious Adverse Events (SAEs) due to Lymphoseek®. There are no known drug interactions leading to contraindications with the use of Lymphoseek®. Post-marketing reports have shown less than 0.12% of subjects experiencing AEs, with the most common one being lack of node localization.

Tc 99m tilmanocept Clinical Study Protocol Number: NAV3-30

2 STUDY OBJECTIVES

2.1 Primary Objective(s)

• Determine the safety and tolerability of Tc 99m tilmanocept in subjects with NASH.

2.2 Secondary Objective(s)

- Determine the three dimensional tessellation localization of Tc 99m tilmanocept by planar and SPECT/CT imaging in subjects with NASH and asymptomatic controls.
- Determine the three dimensional tessellation localization of unfiltered Tc 99m sulfur colloid by planar and SPECT/CT imaging in subjects with NASH and asymptomatic controls.
- Comparison of liver localization distribution tessellation pattern intensity between Tc 99m tilmanocept and unfiltered Tc 99m sulfur colloid

2.3 Exploratory

- Concordance of intrahepatic localization tessellation discrimination of Tc 99m tilmanocept (intrahepatic disease heterogeneity) by SPECT/CT imaging and elastography
- Concordance of intrahepatic localization tessellation discrimination of Tc 99m sulfur colloid (intrahepatic disease heterogeneity) by SPECT/CT imaging and elastography

Confidential Page 33 of 71

3 OVERVIEW OF METHODOLOGY AND DESIGN

3.1 Overall Study Design

This is a prospective, open-label, multicenter, safety, comparative study of IV administered Tc 99m tilmanocept and unfiltered Tc 99m sulfur colloid in the detection of and assessment of three dimensional tessellation localization to the liver in subjects with and without moderate to severe NASH by planar and SPECT/CT imaging.

On Day 0, subjects will receive IV administration of 8.0 mCi of unfiltered Tc 99m sulfur colloid. Subjects will have planar imaging of the liver followed by SPECT/CT scanning of the abdomen, liver, and spleen at 20 minutes \pm 5 minutes post-administration.

On Day 3, subjects will receive IV administration of 200 μg of tilmanocept at the specified radiolabeled dose of Tc 99m. Subjects will have planar imaging of the liver followed by SPECT/CT scanning of the abdomen, liver, and spleen at three specified time points post-administration: 20 minutes \pm 5 minutes, 75 minutes \pm 15 minutes, and 180 minutes \pm 15 minutes.

The proposed study includes 3 visits and a safety follow-up telephone call: a screening visit for initial determination of eligibility and evaluation of clinical status ("Visit 1"), Day 0 ("Visit 2") the day of unfiltered Tc 99m sulfur colloid administration and imaging, Day 3 ("Visit 3") the day of Tc 99m tilmanocept administration and imaging, and a safety follow-up telephone call 5 ± 3 days following Tc 99m tilmanocept administration.

The Schedule of Events (Appendix 1) contains a list of all study procedures and time points. Study activities are described in detail in Section 7.

Following completion of the first two enrolled NASH subjects, a review meeting will be held to evaluate tilmanocept safety and dose performance.

3.2 Justification for Study Design and Population

This feasibility study is designed to evaluate the safety of Tc 99m tilmanocept and to compare Tc 99m tilmanocept tessellation localization in the livers of subjects with moderate to severe NASH and healthy controls (HCs) to unfiltered Tc 99m sulfur colloid localization. Planar imaging of the liver using a SPECT camera will be combined with SPECT/CT imaging of the abdomen to provide greater resolution of areas of intrahepatic localization.

This study is designed to evaluate the use of Tc 99m tilmanocept as an imaging agent in subjects with biopsy-confirmed moderate to severe NASH by evaluating intrahepatic localization tessellation.

3.3 Protocol Adherence

Strict adherence to all specifications outlined in this protocol is required for all aspects of the study conduct; the investigator may not modify or alter the procedures described in this protocol. If protocol modifications are necessary, all alterations that are not solely of an

Confidential

administrative nature require a formal protocol amendment for the involvement of Institutional Review Board(s) (IRB(s)).

If an investigator has deviated from the protocol in order to eliminate an immediate hazard to subjects or for other inevitable medical reasons, the investigator shall document all such deviations, including the reasons thereof, and submit the document to the sponsor and the IRB as applicable.

3.4 Study Duration

Subjects will be "on study" for up to 57 days depending on the duration of the screening window (up to 45 days).

4 STUDY POPULATION

4.1 Eligibility

Subjects who fulfill all respective inclusion and none of the respective exclusion criteria will be eligible for enrollment into the study. All inclusion/exclusion criteria must be verified before a subject may be considered eligible for administration of unfiltered Tc 99m sulfur colloid and imaging (Day 0 procedures). A subject will be considered enrolled in the study on the morning of study Day 0 when they arrive at the study site and receive Tc 99m sulfur colloid via IV administration. Written and dated (with time noted) informed consent will be obtained from all subjects. A subject who withdraws consent prior to arrival at the study site on Day 0 will be considered a screen failure.

4.1.1 Inclusion Criteria

ALL SUBJECTS:

- 1. The subject has provided written informed consent with HIPAA (Health Information Portability and Accountability Act) authorization before the initiation of any study-related procedures.
- 2. The subject is ≥ 18 years of age at the time of consent.
- 3. The subject has a body mass index (BMI) between 18 and 45.

CONTROL SUBJECTS:

- 4. The subject is deemed to be clinically free of any infectious/inflammatory disease(s) for at least 4 weeks prior to the consent date.
- 5. The subject has not taken any antibiotics for at least 4 weeks prior to the consent date.

NASH SUBJECTS:

- 4. The subject has biopsy-confirmed NASH within 12 months prior to enrollment.
- 5. The subject has a NAFLD Activity Score (NAS) of \geq 4, with a score of at least 1 for each steatosis, lobular inflammation, and hepatocyte ballooning.
- 6. The subject has fibrosis staging of F3-F4.

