4.1.2 Exclusion Criteria

ALL SUBJECTS:

- 1. The subject is pregnant or lactating.
- 2. The subject size or weight is not compatible with imaging per the investigator.
- 3. The subject has received radiation therapy or chemotherapy or has a previous diagnosis of cancer other than basal cell carcinoma.
- 4. The subject has renal insufficiency as demonstrated by a GFR of < 60 mL/min.

Confidential

- 5. The subject has a chronic or persistent infection or has any condition that would, in the opinion of the examining physician, preclude their participation.
- 6. The subject has a known allergy to or has had an adverse reaction to dextran exposure.
- 7. The subject has received an investigational product within 30 days prior to the Tc 99m sulfur colloid administration.
- 8. The subject has received any radiopharmaceutical within 7 days prior to the administration of Tc 99m sulfur colloid.
- 9. The subject is HIV positive.
- 10. The subject has a history of alcohol abuse or currently consumes alcohol in excess of 3 drinks/day for men or 2 drinks/day for women.
- 11. The subject has hepatitis B or C.

CONTROL SUBJECTS:

- 12. The subject has hepatic insufficiency as demonstrated by ALT (alanine aminotransferase [SGPT]) or AST (aspartate aminotransferase [SGOT]) greater than two times the upper limit of normal (ULN).
- 13. The subject has been diagnosed with NASH, NAFLD, or other chronic liver disease.
- 14. The subject has been diagnosed with metabolic syndrome or Type I or II diabetes.

NASH SUBJECTS:

- 12. The subject has any chronic liver disease aside from NASH/NAFLD.
- 13. The subject has uncontrolled diabetes as indicated by an A1c >9% within the 3 months prior to enrollment.

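### Control criteria 4 and 5 end their 4 clean weeks at consent rather than at Day 0, so after 28 or more days of screening they cover none of the 4 weeks before imaging

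*Combined protocol and SAP*

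**What the plan says.** Section 4.1.1 sets two dated health requirements for controls, repeated in the synopsis. Criterion 4: "The subject is deemed to be clinically free of any infectious/inflammatory disease(s) for at least 4 weeks prior to the consent date". Criterion 5: "The subject has not taken any antibiotics for at least 4 weeks prior to the consent date".

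Consent is obtained at Visit 1, on any day from Day -45 to Day -1 (Section 7.2.1). Sulfur colloid is given and imaged on Day 0, and tilmanocept on Day 3. Section 4.1 adds: "All inclusion/exclusion criteria must be verified before a subject may be considered eligible for administration of unfiltered Tc 99m sulfur colloid and imaging". It also fixes enrollment: "A subject will be considered enrolled in the study on the morning of study Day 0 when they arrive at the study site", with the sulfur colloid injection completing it.

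The other dated look-backs in Sections 4.1.1 and 4.1.2 end later than consent:

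- Exclusion 7: "The subject has received an investigational product within 30 days prior to the Tc 99m sulfur colloid administration".
- Exclusion 8: "The subject has received any radiopharmaceutical within 7 days prior to the administration of Tc 99m sulfur colloid".
- NASH inclusion 4: "The subject has biopsy-confirmed NASH within 12 months prior to enrollment".
- NASH exclusion 13 dates the A1c limit to the 3 months before enrollment.

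The only undated infection rule is exclusion 5: "The subject has a chronic or persistent infection or has any condition that would, in the opinion of the examining physician, preclude their participation".

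**The concern.** The two criteria show that the sponsor wants controls without recent infection, inflammation or antibiotic use. The protocol gives a reason: the tracer binds CD206 on activated macrophages, which gather where there is inflammation (Sections 1.1 and 1.4.2). What matters for the images is the subject's state on Day 0 and Day 3, yet the clean period is measured back from a date that can lie weeks earlier. A control who falls ill or takes antibiotics between consent and imaging satisfies both criteria as written.

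Controls are the reference for the secondary imaging results. The synopsis compares all results with control-group statistics at each time point, and Section 9.5.3 pools the control voxel intensities into one density estimate. If option 2 in Section 5.2 is followed, the second review meeting also compares NASH subjects with three controls. With so few, one unsuitable control carries visible weight.

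**Working it through.** **Inputs.** Clean window: 4 weeks = 28 days, ending the day before consent (Section 4.1.1). Consent: Day -45 to Day -1 (Section 7.2.1). Imaging: Day 0 and Day 3 (Section 3.1). Last contact: Day 8 ± 3, so Day 11 at the latest (Section 7.2.4).

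**The plan's own figure.** Section 3.4 gives up to 57 days on study. Counting Day -45 to Day 11 inclusively: 45 + 1 + 11 = 57. This reproduces, and confirms that a 45-day screening period is intended to be possible.

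**Gap from consent to imaging.** Let s be the days from consent to Day 0, from 1 to 45. The gap to sulfur colloid is s (1 to 45 days), and the gap to tilmanocept is s + 3 (4 to 48 days).

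**Coverage.** The criteria guarantee days -(s + 28) to -(s + 1).

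- The 28 days before Day 0 are Day -28 to Day -1. Overlap = max(0, 28 - s).
- The 28 days before Day 3 are Day -25 to Day 2. Overlap = max(0, 25 - s).

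| s | Covered before Day 0 (of 28) | Covered before Day 3 (of 28) |
|---|---|---|
| 1 | 27 | 24 |
| 7 | 21 | 18 |
| 14 | 14 | 11 |
| 21 | 7 | 4 |
| 25 | 3 | 0 |
| 27 | 1 | 0 |
| 28 to 45 | 0 | 0 |

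Coverage before Day 0 is zero for s = 28 to 45, which is 45 - 28 + 1 = 18 of 45 permitted lengths. Before Day 3 it is zero for s = 25 to 45, which is 45 - 25 + 1 = 21 of 45. If the consent day itself is counted as clean, each threshold moves by one day (to 29 and 26), without changing the substance.

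**Same 28 days, ending at sulfur colloid injection.** The guaranteed days become Day -28 to Day -1 at every s: 28 of 28 before Day 0, and 28 - 3 = 25 of 28 before Day 3.

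**Anchors.** Of the six dated look-backs in Sections 4.1.1 and 4.1.2, two run to sulfur colloid injection and two to enrollment, which is Day 0. Only control criteria 4 and 5 stop at consent.

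**Number of controls (Section 5.2).**

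| Path | Controls at 8.0 mCi | Controls at 2.5 mCi | Total |
|---|---|---|---|
| Option 1 | 0 | 3 | 3 |
| Option 2, stops at second review | 3 | 0 | 3 |
| Option 2, continues | 3 | 3 | 6 |

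One control is therefore 1/3 of the reference within any dose group that has controls, and 1/6 only if option 2 continues and both groups are pooled.

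**The case against.** **No stated window is breached.** A reader might infer from the zero-coverage rows that the plan breaks its own 28-day rule. It does not: no section demands 28 clean days before Day 0 or Day 3. That yardstick is the criteria's own length moved to the imaging date. This stands, and the point is limited to an inconsistent anchor.

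**Different purposes can justify different anchors.** Earlier investigational products and radiopharmaceuticals relate naturally to dosing, and the two NASH criteria date disease evidence. So four of six is not proof of error. But freedom from infection also matters at imaging, and the protocol offers no reason for ending it at consent. Section 8.1.1 describes controls as lacking evidence of liver or inflammatory disease when enrolled, which is Day 0.

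**Illness present at imaging is partly handled.** Exclusion 5 has no consent anchor and leaves room for the physician's judgement. Criteria must be verified before Day 0 procedures. Controls are clinically assessed for absence of liver and inflammatory disease (Section 4.2). Adverse events, medications and temperature are checked before each injection (Sections 7.2.2.1 and 7.2.3.1). The investigator may withdraw a subject (Section 4.3). It would therefore be wrong to read the controls as unprotected. These safeguards are discretionary, however. Verifying a consent-anchored criterion does not move its anchor, and nothing makes a new acute infection or antibiotic course disqualifying. What remains is mainly illness recently resolved, an antibiotic course already completed, or illness left to judgement.

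**No consequence is shown.** The study is descriptive, no formal tests are planned, and individual-subject densities will be available (Section 9.5.3), so an affected control could be identified. This stands and keeps the severity low.

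**Conclusion.** The point holds as a low-severity inconsistency. As anchored, criteria 4 and 5 guarantee between 27 and 0 of the 28 days before Day 0, and between 24 and 0 of the 28 days before Day 3, depending only on how long screening lasts.

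Three stronger readings are not supported:

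- 18 of 45 is a count of permitted screening lengths. The documents give no distribution of s, so it is not a probability that a control goes uncovered.
- The NASH-versus-control comparison cannot be called biased. The documents do not say whether acute illness outside the liver, or antibiotics, changes liver uptake of either tracer, so size and direction are unknown.
- Not every dose group has three controls. Under option 1 the 8.0 mCi group has none.

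The conclusion rests on counting 4 weeks as 28 days and on excluding the consent day from the window. The primary safety endpoint is unaffected.

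**What to change.** In Section 4.1.1 and the synopsis, let the windows in control criteria 4 and 5 end at sulfur colloid injection instead of at consent, as exclusions 7 and 8 already do. Confirm both at the adverse event and medication review that already takes place on Day 0 before dosing. The three days from Day 0 to Day 2 would still rest on the existing Day 3 review.

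The cost is wording in two criteria in two places, with no new visit or procedure. The records mostly exist but not entirely. Medications are documented from 30 days before screening (Section 6.1). Adverse events are recorded only from Visit 1 (Section 8.4.1.1), so when screening is shorter than 28 days, earlier illness must come from the medical history or be confirmed at screening. Section 7.2.1 asks for onset month and year only for conditions still active, so the end date of a resolved infection should be asked for explicitly.

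There may be a few more control screen failures, some found on the morning of Day 0 after the screening tests and elastography are done. With consent on Day -45, a new illness or antibiotic course still fits the window if the first clean day is Day -28 or earlier, that is no later than 45 - 28 = 17 days after consent. A later one does not.

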4.1.2 Exclusion Criteria

ALL SUBJECTS:

- 1. The subject is pregnant or lactating.
- 2. The subject size or weight is not compatible with imaging per the investigator.
- 3. The subject has received radiation therapy or chemotherapy or has a previous diagnosis of cancer other than basal cell carcinoma.
- 4. The subject has renal insufficiency as demonstrated by a GFR of < 60 mL/min.

Confidential

- 5. The subject has a chronic or persistent infection or has any condition that would, in the opinion of the examining physician, preclude their participation.
- 6. The subject has a known allergy to or has had an adverse reaction to dextran exposure.
- 7. The subject has received an investigational product within 30 days prior to the Tc 99m sulfur colloid administration.
- 8. The subject has received any radiopharmaceutical within 7 days prior to the administration of Tc 99m sulfur colloid.
- 9. The subject is HIV positive.
- 10. The subject has a history of alcohol abuse or currently consumes alcohol in excess of 3 drinks/day for men or 2 drinks/day for women.
- 11. The subject has hepatitis B or C.

CONTROL SUBJECTS:

- 12. The subject has hepatic insufficiency as demonstrated by ALT (alanine aminotransferase [SGPT]) or AST (aspartate aminotransferase [SGOT]) greater than two times the upper limit of normal (ULN).
- 13. The subject has been diagnosed with NASH, NAFLD, or other chronic liver disease.
- 14. The subject has been diagnosed with metabolic syndrome or Type I or II diabetes.

NASH SUBJECTS:

- 12. The subject has any chronic liver disease aside from NASH/NAFLD.
- 13. The subject has uncontrolled diabetes as indicated by an A1c >9% within the 3 months prior to enrollment.

4.2 Recruitment

Subjects will be recruited from gastroenterology practices in accordance with the inclusion and exclusion criteria listed above. Potentially suitable subjects will be asked by their treating physician about their willingness to participate in this study. Healthy, "NASH-free" subjects (controls) may be recruited via IRB approved advertisements and clinically assessed for the "absence" of liver and inflammatory diseases.

4.3 Withdrawal

In accordance with the Declaration of Helsinki, each subject is free to withdraw from the study at any time and without providing a reason.

A subject who withdraws consent prior to administration of Tc 99m sulfur colloid at the study site on Day 0 will be considered a withdrawn subject.

Should a subject withdraw after administration of the investigational product, all efforts will be made to complete and report the observations up to the time of withdrawal as thoroughly as

Confidential Page 37 of 71

Clinical Study Protocol Number: NAV3-30

possible. An explanation should be given of why the subject is withdrawing or being withdrawn from the study.

The investigator may withdraw a subject from the study at any time at the discretion of the investigator for any of the following reasons:

- A protocol violation occurs
- A serious or intolerable AE occurs
- A clinically significant change in a laboratory parameter occurs
- At the investigator's/sponsor's discretion as long as it is in the best interest of the subject
- The sponsor or investigator terminates the study
- The subject requests to be discontinued from the study

